After written consent is obtained, the pre-COVID-19 and baseline information will be collected. Their COVID-19 information will be collected via face-to-face interview or telephone follow-up or by email. 1, 3 and 6-month data post-discharge will be collected via telephone follow-up interview with the patient or e-form completed by the patient.

Quality of life assessment tools

SF-12

The 12-Item Short Form Health Survey is an abbreviated version of the 36-Item Short Form Health Survey. It is a widely used, international, validated survey for investigating health-related quality of life in a variety of both acute and chronic conditions. The survey instrument has eight domains: physical functioning, physical role, bodily pain, general health, vitality, social functioning, emotional role, and mental health. Each domain is measured on a 0-100 scale. A higher score correlates with a higher quality of life. The survey generates a Mental Component Summary (MCS) and a Physical Component Summary (PCS). A Chinese version of the survey, the 12-item Chinese (Hong Kong) Short Form Health Survey (version 2) (SF-12v2 (HK)) has been previously validated and used in Hong Kong.²¹ We will be using the four week recall (standard) version of the SF012v2(HK).

EQ-5D-5L

The EQ-5D-5L is a brief health status measure that comprises of five domains: mobility, self-care, pain, usual activities, and psychological status. EQ-5D-5L has been validated in Hong

Kong, recently for use in patients with chronic obstructive pulmonary disease.²³

Return to work status

Patients' pre-COVID-19 infection work status will be compared to their post-infection status. The type of employment, salary and each patients' subjective work experiences before and after infection will be queried.

Definitions

COVID-19 = Coronavirus Disease 2019, the new disease pandemic caused by the SARS-CoV-2 virus.

CUHK = The Chinese University of Hong Kong

EQ-5D-5L = EuroQol Five Domain survey, one of the two main survey instruments we will use to quantitatively judge quality of life for enrolled study subjects.

NTEC = New Territories East Cluster, a grouping of healthcare facilities in northeast Hong Kong.

PWH = Prince of Wales Hospital, the largest acute care hospital in the Hong Kong Hospital Authority's New Territories East Cluster as well as the major teaching hospital for the Chinese University of Hong Kong's medical school.

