SARS = Severe Acute Respiratory Syndrome, the disease associated with the coronavirus epidemic of 2003 (not to be confused with SARS-CoV-2, which is the virus causing COVID-19 disease).

SARS-CoV-2 = Severe Acute Respiratory Syndrome Coronavirus 2, the virus identified as the causative organism of the COVID-19 disease.

SF-12 = The 12-Item Short Form Health Survey, one of the two main survey instruments we will use to quantitatively judge quality of life for enrolled study subjects. We will use the SF-12v2(HK) version of the SF-12, which has been specifically validated for use in Hong Kong.

Study design

Recruitment

All adult COVID-19 patients aged ≥ 18 years who present to the infectious diseases specialist outpatient follow-up clinic at PWH will be screened for inclusion in this study by research assistants involved in this study.

First interview

After consent, the pre-COVID-19 assessments of SF-12v2(HK) and EQ-5D-5L will be obtained

by face-to-face interview or by phone interview by a research assistant or by e-form completed by the patient. The interview process should take no longer than 10 minutes. The questionnaire may be completed by a proxy if the patient is unable to respond to the interviewer. Work status one month prior to COVID-19 diagnosis will be determined at this time as well.

Follow-up interviews

The SF-12v2(HK) and EQ-5D-5L will be obtained by telephone interview from the patient or e-form completed by the patient. The follow-up measures will be performed at 1, 3, and 6-months after date of recovery by a research assistant.

Studies have found differences between quality of life assessments completed by the patient or by proxy. In previous studies, it has been shown that when using EQ-5D-5L as an assessment tool, there is good agreement on the domain of self-care, but only a “fair” agreement on domains such as mobility, pain and anxiety were observed between the patients and caregiver rating.²⁴ However, if all proxy responses were excluded, quality of life for survivors of sepsis with communication problems would not be included, which would be a significant methodological and ethical problem. Thus, in this proposed study, the questionnaire may be completed by a proxy if the patient is unable to respond to the interviewer (e.g. patients with dementia or stroke). A subgroup analysis will be performed accordingly.

Data processing and analysis

Outcomes

Primary outcome

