COVID-19 is still an incompletely understood disease. We will perform secondary analyses on the data to allow us to focus on specific groups and to adjust for variability. We will consider the severity of COVID-19 by examining each patient's clinical record, number of hospital days admitted, number of days spent in the intensive care unit, number and severity of organ(s) dysfunction, co-infections, pathogen(s) identified, pre-COVID-19 health status and pre-existing conditions. It is anticipated that there will be marked changes and differences in health status and functional outcome depending on patient age. Comparisons of quality of life between four time points (pre-sepsis, hospital stay, 3-months and 6-months after discharge) will be assessed using paired t-test or Wilcoxon (W) tests as appropriate.

Multivariate logistic regression analysis

All parameters will be entered into a multiple logistic regression model and used to evaluate associations and account for variation. Multiple logistic regression adjusts for variable interactions and will be used to identify predictors of quality of life in COVID-19 patients during follow-up.

References

1. World Health Organization. *Situation Report-78 HIGHLIGHTS.*; 2020. https://www.who.int/docs/default-source/coronavirus/situation-reports/20200407-sitrep-78-covid-19.pdf?sfvrsn=bc43e1b_2. Accessed April 10, 2020.
2. Centre for Health Protection of the Department of Health of the Hong Kong SAR. *Countries/Areas with Reported Cases of Coronavirus Disease-2019 (COVID-19).*; 2020. https://www.chp.gov.hk/files/pdf/statistics_of_the_cases_novel_coronavirus_infection_en.pdf. Accessed April 10, 2020.
5. Hui DS. Severe acute respiratory syndrome (SARS): Lessons learnt in Hong Kong. *J Thorac Dis.* 2013;5(SUPPL.2). doi:10.3978/j.issn.2072-1439.2013.06.18

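### The pre-COVID questionnaire may be face-to-face but follow-up may not, and the respondent may change, so the secondary paired comparisons can mix real change with a change of mode or respondent

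*Combined protocol and SAP*

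**What the plan says.** Under Study design, First interview, the pre-COVID SF-12v2(HK) and EQ-5D-5L are obtained "by face-to-face interview or by phone interview by a research assistant or by e-form completed by the patient". Under Follow-up interviews the modes are fewer: "The SF-12v2(HK) and EQ-5D-5L will be obtained by telephone interview from the patient or e-form completed by the patient". The Methods section agrees: data at 1, 3 and 6 months come from a "telephone follow-up interview with the patient or e-form completed by the patient".

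On the respondent, First interview states: "The questionnaire may be completed by a proxy if the patient is unable to respond to the interviewer". Follow-up interviews repeats the rule ("in this proposed study, the questionnaire may be completed by a proxy if the patient is unable to respond to the interviewer"), although the sentence on modes under that same heading speaks only of the patient. That section also reports that patient and proxy ratings differ, with "only a “fair” agreement on domains such as mobility, pain and anxiety were observed between the patients and caregiver rating", and promises a subgroup analysis for proxy answers without defining it.

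Secondary analyses plans comparisons across time points, including a pre-illness one, which "will be assessed using paired t-test or Wilcoxon (W) tests as appropriate". That section labels the pre-illness point as pre-sepsis; I read it as the pre-COVID questionnaire. The primary outcome is the SF-12v2(HK) summary scores at six months. The Hypotheses section compares survivors with Hong Kong norms, and Primary analysis adds earlier SARS, sepsis and trauma survivors.

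No section requires the same mode or respondent throughout, plans to record mode, or adjusts for either in the paired tests.

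**The concern.** A paired test removes stable differences between patients. It does not remove a shift that arises because the two members of a pair were collected differently. Patients whose first questionnaire is face-to-face cannot repeat that mode later, and the forced change always runs in one direction. If the change of mode moves scores systematically, the shift does not average out across those patients and appears as a change in quality of life.

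The respondent raises a similar problem. A proxy may answer when the patient cannot, so a proxy may complete one questionnaire and the patient another. Because proxy use depends on the patient's condition, such a switch can coincide with recovery or deterioration, which is what the comparison is meant to measure. An undefined proxy subgroup does not say where a patient with mixed respondents belongs.

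At stake is how the secondary pre-COVID versus follow-up comparisons are read. If mode and respondent are not recorded at the time, they may not be recoverable, and nobody could later separate an artefact of collection from a real change.

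**Working it through.** **Modes and respondents side by side**

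| | Pre-COVID questionnaire | 1, 3 and 6 months |
|---|---|---|
| Face-to-face | allowed | not listed |
| Telephone | allowed | allowed |
| E-form | allowed | allowed |
| Proxy, if the patient cannot answer | allowed | allowed by the restated rule; the mode sentence names only the patient |

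A face-to-face start forces a change. A telephone or e-form start does not, though nothing prevents one. A 3 versus 6-month pair has no face-to-face mismatch, although telephone and e-form may still alternate.

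**Size.** The plan has no figure on this point to reproduce: it gives no mode effect, no direction and no SD of change. What follows is an illustration.

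Inputs from the documents:
- Two-sided significance level of 0.05 (Statistical analysis, General).
- Number of patients: 100 (Methods) or about 200 (Sample size calculation). The counts in the latter section give (89 + 117) × 0.80 = 164.8, which matches neither, so I ran 100 and 200 to bracket it.

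Assumptions not in the documents:
- SD of within-patient change: 10 points.
- Shift m when mode (or respondent) changes: 1, 2 or 3 points, all in the same direction.
- Share of patients who switch, f: 0, 25%, 50% or 100%.
- No true change and no attrition.

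Formulas:
- Bias in mean change = f × m.
- SD allowing for the mixture = √(10² + f(1 − f)m²).
- λ = bias × √n / SD.
- Rejection rate = 1 − Φ(1.96 − λ) + Φ(−1.96 − λ).

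Example with n = 100, f = 0.5, m = 3: bias = 1.5; SD = √(100 + 0.25 × 9) = 10.11; λ = 1.5 × 10 / 10.11 = 1.483; rate = 1 − Φ(0.477) + Φ(−3.443) = 0.317.

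Rejection rates of the nominal 5% test:

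| Share switching | Bias, m = 1 to 3 | n = 100: m = 1, 2, 3 | n = 200: m = 1, 2, 3 |
|---|---|---|---|
| 0 | 0 | 5.0%, 5.0%, 5.0% | 5.0%, 5.0%, 5.0% |
| 25% | 0.25 to 0.75 | 5.7%, 7.9%, 11.5% | 6.4%, 10.9%, 18.3% |
| 50% | 0.5 to 1.5 | 7.9%, 16.9%, 31.7% | 10.9%, 29.1%, 55.5% |
| 100% | 1 to 3 | 17.0%, 51.6%, 85.1% | 29.3%, 80.7%, 98.9% |

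With m = 0 every cell is 5%. The formula is symmetric, so a shift of the opposite sign gives the same rates. A larger study makes the false-positive rate worse, because the bias stays fixed while the standard error shrinks.

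**The case against.** **Only a secondary analysis is touched.** This stands. A reader might infer that the main result is compromised. The documents do not support that: the primary outcome is a six-month score compared with external data, not a change from the pre-COVID questionnaire.

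**The mechanism is incomplete.** One plausible reason for a shift is that people answer an interviewer in person more favourably than they complete a form alone. That fits a move from face-to-face to e-form. A telephone interview is still led by an interviewer, and the documents give no reason to expect a shift from face-to-face to telephone. Patients unavailable for telephone follow-up are excluded, so telephone should be open to everyone enrolled. A reader might infer that the design manufactures a decline. Neither the existence nor the direction of a mode effect is in the documents.

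**The large percentages are a worst case.** This stands too. Rates of 52% and 85% need every patient to switch. A reader might infer that everyone recruited at the clinic must do so, but telephone and e-form are open at the first interview. Only patients actually interviewed face-to-face are forced to change.

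**Proxy answers are conditional.** A reader might infer that patient and proxy can alternate freely. They cannot: a proxy may answer only when the patient cannot. The plan's examples are dementia and stroke, where the inability may persist, and excluding patients who cannot give written consent may keep such cases few. The plan also acknowledges the disagreement and promises a subgroup analysis. That is a partial safeguard for respondent type, but it does not cover a switch within a pair and does nothing for mode.

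**A larger limitation remains.** The pre-COVID score is recalled after the illness whatever the mode, and harmonising collection does not change that.

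These points reduce the importance of the concern. They do not remove the mismatch in permitted modes or the absence of any rule or record.

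**Conclusion.** The concern holds for the secondary paired comparisons of pre-COVID with follow-up scores. Following the plan as written forces a one-way change of mode on each patient first interviewed face-to-face. It also permits a change of respondent, although the plan itself reports limited patient-proxy agreement on some domains.

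The size cannot be known from the documents. Under the assumptions above with 100 pairs, the false-positive rate ranges from about 6-12% with a quarter of patients switching to 17-85% with all switching. It stays at 5% if there is no mode effect. These figures show sensitivity and are not predictions. No size can be attached to respondent switching beyond the same illustration.

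This is a low-cost improvement to secondary analyses. It is not a flaw in the primary comparison.

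**What to change.** - **First interview and Follow-up interviews:** record mode and respondent at every assessment. Where feasible, take the first questionnaire by the mode (telephone or e-form) the patient will use at follow-up, and keep mode and respondent constant thereafter. Reconcile the follow-up wording so that it is clear whether a proxy may answer.
- **Proxy subgroup:** define it by visit, so that patients whose respondent changes are identified.
- **Secondary analyses:** repeat the paired pre-COVID comparisons in pairs with the same mode and, separately, in pairs with the same respondent.

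The cost is two form fields and smaller sensitivity sets. The same-respondent set is also selected, because regaining the ability to answer is tied to recovery, so it should be read only as a sensitivity analysis. Matching mode may mean a separate baseline call for a patient seen in clinic who does not use e-forms, which is why the rule says where feasible. Removing the in-person option altogether is not needed. If it is kept, recording both fields and running the sensitivity analyses is the minimum. None of this addresses the recalled nature of the pre-COVID score.

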By identifying overall COVID-19 quality of life as well as specific associations or differences between COVID-19 and baseline local quality of life values, we hope to be able to provide evidence-based conclusions to medical practitioners trying to achieve the best quality of life for patients recovering from COVID-19.

Hypotheses

The null hypothesis is that recovered COVID-19 patients have no difference in quality of life compared to a normal control (baseline Hong Kong quality of life norms).

The alternative hypothesis is that there is a difference in quality of life measures between recovered COVID-19 patients and a normal control.

Plan of Investigation

Subjects

All adult patients aged ≥ 18 years who present to the infectious diseases specialist outpatient follow-up clinic at PWH will be screened for inclusion in this study. The inclusion criteria are age ≥ 18 years, laboratory-confirmed COVID-19 infection with SARS-CoV-2, and patients who agree to follow-up for up to six months following their first interview.

Exclusion criteria:

Patients aged below 18 years will be excluded.

Patients will be excluded if they meet ANY of the following criteria:

Patients or their next of kin are unable to communicate in Chinese or English,

Unwilling or unable to provide written informed consent,

or Patients who will not be available for telephone follow-up at the scheduled times.

We will record all patients who are not enrolled and the reasons for exclusion.

Sample size calculation

As of April 10, 2020, in the NTEC Hospital Authority cluster there have been 89 patients

admitted to PWH (of which 17 patients have already been discharged) and 117 admitted to United Christian Hospital with 42 discharged so far.²² Both PWH and United Christian Hospital's COVID-19 patients will follow-up at the PWH infectious diseases specialist outpatient follow-up clinic. Based on prior studies at PWH with SARS patients, approximately 80% agreed to participate in follow-up studies, so we will likely enroll approximately 200 COVID-19 patients.

Methods

This will be a prospective, observational, multicenter, cohort study. We plan to recruit 100 patients with laboratory confirmed COVID-19 disease who have been discharged from inpatient care or quarantine. Quality of life will be assessed using the SF-12v2(HK) and EQ-5D-5L survey instruments, and their return to work status will be measured up to six months from the date of discharge.

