The primary outcome measure will be the health summary scores from SF-12v2(HK) in COVID patients at six-months post-discharge from hospital.

Secondary outcomes

The secondary outcome measures will include the health status measures of the EQ-5D-5L and return to work status in COVID patients at six-months post discharge from hospital.

Other measures

The required clinical data for patient characteristics and data for investigating each patient’s relative illness severity will be collected at the earliest opportunity after subject enrollment. The final COVID-19 diagnosis and any other final diagnoses will be recorded from the patient’s existing clinical notes. The Hospital Authority’s computerized Clinical Management System (the

system used by all hospitals under Hospital Authority for storing and retrieving patients' data) will be reviewed to identify hospital admissions, emergency department reattendance, lengths of stay (intensive care, step-down units or general wards) and mortality.

Statistical analysis

General

Chi-square and Fisher's exact tests will be used for categorical data while t-tests will be used to compare means of continuous variables. A p value <0.05 will be considered statistically significant and all tests will be two-tailed.

Primary analysis

A univariate and multivariate analysis of the data set will be conducted at six months. SF-12v2 dimensions of survivors of COVID-19 will be compared with data from past survivors of SARS infection, sepsis or trauma. We will also compare this data to the general Hong Kong population summary score data. Data from the EQ-5D-5L survey instrument will be compared using the Chi-square or Fisher's exact tests.

Secondary analyses

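### The primary analysis does not match the primary outcome or the stated hypothesis, and no rule says whether PCS, MCS or either decides the null

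*Combined protocol and SAP*

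**What the plan says.** All references are to the combined protocol and SAP.

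- **Hypotheses:** "The null hypothesis is that recovered COVID-19 patients have no difference in quality of life compared to a normal control". The text goes on to define that control as the baseline Hong Kong norms. No other comparator appears in the hypotheses, and no particular score is named.
- **Primary outcome:** "The primary outcome measure will be the health summary scores from SF-12v2(HK) in COVID patients at six-months post-discharge from hospital".
- **Quality of life assessment tools, SF-12:** the instrument has eight domains, each scored 0 to 100, and yields two summary scores, MCS and PCS.
- **Primary analysis:** "SF-12v2 dimensions of survivors of COVID-19 will be compared with data from past survivors of SARS infection, sepsis or trauma". The next sentence reads: "We will also compare this data to the general Hong Kong population summary score data". The same paragraph then gives a test for the EQ-5D-5L, which the Secondary outcomes section lists as secondary.
- **Statistical analysis, General:** "A p value <0.05 will be considered statistically significant and all tests will be two-tailed".

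The document names no lead score, order of testing, success rule or multiplicity adjustment.

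**The concern.** The outcome, the hypothesis and the analysis should name the same variable and the same comparator. Here the outcome and hypothesis point to the summary scores against Hong Kong norms, while the analysis puts the dimensions against three patient groups first. An analyst who follows the Primary analysis section in order begins with a variable that is not the primary outcome and a comparator that is not in the null. The comparison that does test the null comes second, in a sentence whose subject (*this data*) refers back, grammatically, to the dimensions.

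Even when that sentence is read favourably, the null concerns quality of life in general, and two scores can each speak to it at 0.05. The plan does not say whether PCS, MCS, either or both must differ. Two careful analysts could therefore reach different primary conclusions from the same data, and the 5% level is not kept for the one hypothesis the protocol states.

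**Working it through.** **1. Outcome, hypothesis and analysis side by side**

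| Element | Variable | Comparator |
|---|---|---|
| Hypotheses | quality of life, score not named | Hong Kong norms |
| Primary outcome | summary scores (PCS, MCS) | none stated |
| Primary analysis, first comparison | eight dimensions | SARS, sepsis or trauma survivors |
| Primary analysis, second comparison | *this data* (ambiguous) | Hong Kong population summary scores |
| Primary analysis, third item | EQ-5D-5L (a secondary outcome) | none stated |

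Only the second comparison can address the null, and only if its subject is taken to include PCS and MCS.

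**2. Error rate for the stated null**

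Inputs: two summary scores (SF-12 section), two-sided 0.05 for each (General section), either one taken as enough to reject. The plan states no overall error rate, so there is no figure of its own to reproduce.

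- Independent scores: 1 − (1 − 0.05)² = 1 − 0.9025 = 0.0975, about 9.8%.
- Correlated scores, bivariate normal, P(|Z₁| > 1.96 or |Z₂| > 1.96): 0.095 at correlation 0.3 and 0.091 at 0.5. The documents give no correlation, so these values are assumptions.
- With each score tested at 0.025: 1 − 0.975² = 0.0494 if independent, and lower if correlated.

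**3. Dimension-by-cohort tests, if they were reported as primary**

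Count: 8 dimensions × 3 cohorts = 24 tests. If all were independent, the chance of at least one p < 0.05 with no true difference would be 1 − 0.95²⁴ = 0.708. That overstates it, because one COVID-19 sample serves all three comparisons and the dimensions are correlated.

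A simulation (200,000 runs, no true differences, equally correlated dimensions, shared COVID-19 group) allows for both. It assumes 100 COVID-19 patients, the Methods figure; only the ratio of group sizes matters. The past-cohort sizes and the correlations are not in the documents and are assumed.

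- Three cohorts of 100: 0.66, 0.60, 0.53 and 0.42 at correlations 0, 0.3, 0.5 and 0.7.
- Three cohorts of 1,000: from about 0.5 at correlation 0 down to 0.29 at 0.7.
- One cohort only, if *or* means a single choice (8 tests): 0.34, 0.25 and 0.19 at correlations 0, 0.5 and 0.7. At correlation 0 this agrees with 1 − 0.95⁸ = 0.337.

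These are chances of at least one false positive among tests filed under Primary analysis. They are not error rates for the null in the Hypotheses section.

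**The case against.** The best defence is that the pieces of a sound primary analysis are already there. The Hypotheses section limits the null to Hong Kong norms, so a difference from past SARS, sepsis or trauma survivors cannot reject it. The norms comparison is worded in terms of summary scores, and *this data* can fairly be taken as the SF-12v2 data, which include PCS and MCS. On that reading the primary outcome is tested against the right comparator. The SARS comparison also has a purpose: the background asks whether outcomes are better than those of SARS survivors. The EQ-5D-5L is plainly listed as secondary, so its sentence looks misplaced rather than promoted. Finally, this is an observational cohort whose first aim is to describe quality of life, and joint control of two distinct scores is partly a matter of preference.

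Much of this stands, and it rules out stronger readings that a reader might infer:

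- That almost any pattern of results could be reported as a positive primary finding. No passage makes a single significant dimension decisive, and the probabilities above fall well short of certainty.
- That 42% to 66% is the study's false-positive rate. Those tests do not bear on the stated null, and the figures also rest on an assumed 100 per cohort.
- That the norms comparison cannot be carried out. It is ambiguous, not impossible.

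The objection does not remove the mismatch. The Primary analysis section still puts another variable and other comparators first, and the favourable reading still lacks a rule for PCS and MCS. The observational design is not an answer either, because the protocol itself sets a null hypothesis, a primary outcome and a significance threshold.

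**Conclusion.** The point holds as a mismatch between outcome, hypothesis and analysis, together with a missing decision rule. The text as written gives first place to a comparison that tests no stated hypothesis, so this is an error to correct and not only a detail to add.

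For the stated null the excess is modest: about 9.8% with independent scores and 9.1% at an assumed correlation of 0.5, against a nominal 5%, on the assumption that either score suffices. The larger figures apply only if the dimension-by-cohort tests are presented as primary: roughly 0.3 to 0.66 with three cohorts, or 0.19 to 0.34 with one. They depend on assumed correlations of 0 to 0.7 and, for three cohorts, on assumed cohort sizes of 100 to 1,000.

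**What to change.** Rewrite the Primary analysis section to say:

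- The primary analysis compares six-month PCS and MCS with the Hong Kong norm PCS and MCS, with both sides scored by the same algorithm.
- The two tests are controlled at 5% overall by Holm: the smaller p-value is judged at 0.025 and, if it passes, the larger at 0.05. The null is rejected for the component or components that pass.

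Move the dimension comparisons with the SARS, sepsis and trauma cohorts, and the EQ-5D-5L, to the secondary analyses, reported with confidence intervals. Keep the SARS comparison as a declared secondary question, since the background poses it.

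The cost is a change of wording, with no new data. The smaller p-value must now fall below 0.025 instead of 0.05, which is a small loss of power.

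### Return to work compares each patient's work status before and after infection, but the only test named for categorical data is unpaired Chi-square/Fisher

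*Combined protocol and SAP*

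**What the plan says.** All references are to the combined protocol and SAP.

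- **Return to work status:** patients' "pre-COVID-19 infection work status will be compared to their post-infection status". Type of employment, salary and "subjective work experiences before and after infection will be queried".
- **First interview:** the earlier status comes from the same patients. "Work status one month prior to COVID-19 diagnosis will be determined at this time as well".
- **Secondary outcomes:** these include the "health status measures of the EQ-5D-5L and return to work status in COVID patients at six-months post discharge from hospital".
- **Statistical analysis, General:** after naming Chi-square and Fisher's, the text states that "exact tests will be used for categorical data while t-tests will be used to compare means of continuous variables". Tests are two-sided at 0.05.
- **Primary analysis:** "Data from the EQ-5D-5L survey instrument will be compared using the Chi-square" or Fisher's test. The comparator is not named.
- **Secondary analyses:** "Comparisons of quality of life between four time points (pre-sepsis, hospital stay, 3-months and 6-months after discharge) will be assessed using paired t-test" or Wilcoxon. This is the only paired rule, and it is limited to quality of life.
- **Multivariate logistic regression analysis:** the stated purpose is to find predictors of quality of life, not change in work status.

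No paired method for categorical data is named, and no denominator is given for return to work.

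**The concern.** Each patient supplies both the before and the after value, so the two proportions being compared are not independent. Chi-square and Fisher's test treat them as if they came from two different sets of people. Someone's work status at one time usually predicts their status some months later, so positive correlation is the natural expectation. The unpaired variance is then too large.

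When Chi-square is applied to the before and after proportions, the error under positive correlation is conservative: it produces no excess of false claims. A real fall in employment is more likely to be missed, and the confidence interval is wider than it need be.

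The wording also leaves room for a different mistake. An analyst could run Chi-square on the cross-table of earlier by later status. That tests whether the two are associated, not whether employment changed, and it would usually be significant even with no change at all.

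**Working it through.** **Inputs from the documents.** Two-sided 0.05 (General). On size, Methods says "We plan to recruit 100 patients with laboratory confirmed COVID-19 disease", while the sample size section expects about 200. The section's own inputs give (89 + 117) × 0.80 = 164.8, or about 165, so neither figure is reproduced. That mismatch is a separate matter; 100, 165 and 200 are all used below. The documents give no power, effect size or work rate for this outcome, so there is no stated figure to reproduce.

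**Assumptions.** Proportion working: p1 = 0.80 before, p2 = 0.70 after. Within-patient correlation r from 0 to 0.7.

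**Variance.** With q = 1 − p:

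- Unpaired: (p1q1 + p2q2)/N = (0.16 + 0.21)/N = 0.37/N.
- Paired: (p1q1 + p2q2 − 2r√(p1q1p2q2))/N. Here √(0.16 × 0.21) = 0.1833, so at r = 0.5 this is (0.37 − 0.1833)/N = 0.1867/N, about half the unpaired value.

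**Cell probabilities.** P(working both times) = p1p2 + r√(p1q1p2q2). In the order both / stop / start / neither:

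- r = 0.3: 0.615 / 0.185 / 0.085 / 0.115
- r = 0.5: 0.652 / 0.148 / 0.048 / 0.152
- r = 0.7: 0.688 / 0.112 / 0.012 / 0.188

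**Power by simulation** (40,000 replicates per setting; uncorrected Chi-square on the two proportions versus exact McNemar):

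| r | N=100 | N=165 | N=200 |
|---|---|---|---|
| 0 | 37% vs 31% | 56% vs 51% | 64% vs 60% |
| 0.3 | 35% vs 41% | 57% vs 66% | 67% vs 75% |
| 0.5 | 32% vs 55% | 58% vs 80% | 70% vs 88% |
| 0.7 | 27% vs 81% | 60% vs 97% | 75% vs 99% |

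Fisher's test has less power than Chi-square: 28%, 25% and 18% at N=100 for r = 0.3, 0.5 and 0.7.

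**Other assumed rates, N=100.** For 70% to 60%: 32% vs 27% (r = 0), 29% vs 35% (0.3), 25% vs 47% (0.5), 19% vs 71% (0.7). For a larger fall, 80% to 60%, little is lost: 92% vs 94% (0.3) and 95% vs 99% (0.5).

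**False-positive rate, 80% at both times, N=100.** At r = 0.3, 0.5 and 0.7, Chi-square gives 2.1%, 0.6% and 0.05%; exact McNemar gives 3.0%, 2.8% and 2.2%. Chi-square on the earlier-by-later cross-table rejects 81% of the time at 0.3 and 99.5% at 0.5, although nothing has changed.

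**Worked example, N=100:** 68 work both times, 12 stop, 2 start, 18 neither (correlation 0.65).

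- Chi-square on 80/20 versus 70/30: 200 × (80×30 − 20×70)² / (150 × 50 × 100 × 100) = 2.667, p = 0.10. Fisher p = 0.14.
- Exact McNemar: 2 × P(X ≤ 2), X ~ Bin(14, 0.5) = 2 × 106/16384, p = 0.013.
- Unpaired 95% CI: 0.10 ± 1.96 × √(0.37/100), or −2 to 22 points.
- Paired 95% CI: 0.10 ± 1.96 × √(14 − 10²/100)/100, or 3 to 17 points.

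With weaker correlation (62 / 18 / 8 / 12, correlation 0.33) the Chi-square is the same and exact McNemar gives p = 0.076, so neither is significant. Doubling the first table to N=200 (24 stop, 4 start) gives p = 0.021 and 0.0002, both significant.

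**The case against.** The strongest reply is that the plan never assigns Chi-square or Fisher's to the before/after work comparison. The General paragraph is one generic sentence. It names only t-tests for continuous data, yet the Secondary analyses use paired tests for quality of life, so the authors know how to handle pairing. That is fair as to intent. Even so, the sentence is the only rule that reaches work status, and following it literally gives the wrong test.

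Second, return to work applies most naturally to people who were working beforehand. In that group baseline is constant, McNemar has nothing to test, and the result is a single proportion with an interval. Chi-square or Fisher's would then be right for comparing that proportion between patient groups. This stands, and it is why the denominator must be stated. It does not remove the problem, because the Return to work status section sets out a before/after comparison without restricting it to those employed.

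Third, the size of the loss rests on assumed rates and correlation. A correlation of 0.7 is close to the maximum for these margins, (0.70 − 0.56)/0.1833 = 0.76. The gain is small at 0.3, absent at zero and reversed if the correlation is negative. This also stands, so the figures are a range and not a forecast.

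Finally, this is one secondary outcome of an observational cohort, and the test could be corrected at analysis without touching conduct. That limits the importance, but a test chosen after the data are seen is weaker than one named in advance.

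**Conclusion.** The concern holds. The plan sets up a paired categorical comparison for a secondary outcome, and its only applicable rule leads to tests for independent samples. Under an assumed fall from 80% to 70%, with 100 patients and correlation 0.3 to 0.7, Chi-square gives up roughly 6 to 54 percentage points of power against exact McNemar. At 200 patients the gap is roughly 8 to 24 points. There is no loss at zero correlation and little for a fall of 20 points. The risk is a missed effect and an over-wide interval, not a false claim, unless the cross-table is tested by mistake. The primary outcome is unaffected.

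For EQ-5D-5L there is only an ambiguity: one section gives Chi-square/Fisher without naming a comparator, and another gives paired tests for quality of life over time.

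**What to change.** In the General paragraph of the statistical analysis section, add wording such as:

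> Pre- versus post-infection work status at six months will be tested with McNemar's exact test (Bowker or Stuart-Maxwell if there are more than two categories), with a 95% confidence interval for the paired difference. The proportion back at work among patients employed one month before diagnosis will be reported descriptively with a 95% confidence interval. Chi-square and Fisher's exact tests will be used for comparisons between different groups of patients.

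In the worked example with 12 stopping and 2 starting, the descriptive proportion would be 68/80 = 85% (Wilson 95% CI 76% to 91%).

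Add one line on EQ-5D-5L to settle the ambiguity: the paired t-test/Wilcoxon rule governs change within patients, and the Chi-square/Fisher rule governs comparisons between groups.

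The cost is analysis-plan wording only. Work status before and after infection is already to be collected from the same patients, so no new data, visits or recruitment are needed. The change should be made before the six-month data are analysed.
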